5.2. SNDS COHORT

5.2.1. INCLUSION CRITERIA

- Male Gender
- Patients hospitalized for transurethral surgery for first line treatment of symptomatic BPH in the same period as patients of the PUL and TURP/LASER cohorts (i.e. hospitalisation with the main diagnosis ICD-10 code N40 and the surgical procedure codes JGFE023 for TURP, JGFE365 for HLE and JGNE171 for GLV);
- Affiliated to a French health insurance system

5.2.2. EXCLUSION CRITERIA

- Patients hospitalized in one of the 7 investigational centers
- Patients with a previous BPH procedure previous pelvic surgery or irradiation, history of prostate or bladder cancer (2-year database history and/or Long term disease registration)
- Patients with biopsy of the prostate within the past 6 weeks
- Patients with short life expectancy based on a Charlson Comorbidity Index ≥ 10 (this threshold reflects the presence of metastasis or an equivalent health condition) (cf. Bannay and al., 2015).

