1.1.2.3. PUL (Urolift) in the French market

In France, the cost of each PUL implant is about €500 and a mean of 4 implants are needed in each surgical procedure. In the French healthcare system, these costs could not be financed by the hospital itself, as it would be more costly than the incomes related with the hospital stay (the mean income of hospitalization for this kind of treatment is about €2253 in 2019). Very few patients would be willing to pay for it. Reimbursement of the implants by the French healthcare social insurance is therefore needed for the distribution of PUL in France. To ensure reimbursement of the implants in addition to the tariff of the hospital stay, Urolift should obtain ASA 3 statement by the HAS. To date there is very little clinical experience of Urolift in France; real life data are not sufficient and economic evaluation of Urolift in the setting of the French healthcare system is missing. These data are needed to support the reimbursement file at the HAS.

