1.3. JUSTIFICATION OF THE METHODOLOGICAL CHOICES

A two-phases economic evaluation

Randomized controlled trials were yet conducted and the remaining question is the cost effectiveness of PUL compared to other transurethral procedure in French daily practice. That's the reason why, we decided to propose an economic evaluation as the primary objective of this study.

In order to provide all pertinent clinical and economical information comparing PUL and TURP/laser surgery over a long-term follow-up period in the French context, we propose to conduct a study in two phases.

1-In the first phase we will prospectively compare a cohort of patients treated with PUL to another cohort of patients treated with TURP/laser during one year follow-up. This part of the study will enable us to gather real-life unknown information on the use of Urolift in French hospitals daily practice and organisation (number of implants needed, length and cost of surgery, length of hospital stay...) and to collect quality of life and clinical data from French population.

2- As some consequences of the surgery, as well as differences between healthcare consumptions, can occur even after 4 months and 1 year, and because it is difficult to pursue the clinical trial over 1 year without too many lost for follow-up patients, we decided to work on health databases for the second part of this study. This second phase will cover a 3-years follow-up by analysing healthcare resources utilization in each cohort using the French nationwide claims database, the SNDS. The comparison between PUL and TURP/Laser procedures will be strengthened by a complementary analysis performed between the PUL cohort and a matched cohort of patients identified in the SNDS database with the same baseline characteristics but treated with transurethral procedures. The matching process (based on a hdDRS) and the statistical methods of adjustment will overcome the absence of randomization in the initial process of patients' assignment to the PUL or TURP cohort.

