1.6. JUSTIFICATION OF THE LOW LEVEL OF INTERVENTION

In 2017, the CNEDiMTS (HAS) performed a review of all available publications regarding Urolift device in order to assess its relevance in France in comparison with available standard of care (TURP).

The CNEDiMTS (HAS) performed a comprehensive review of the results of the LIFT study with 3 years follow-up data, of the BPH-6 Study, of an economic evaluation performed by the NICE in the UK, and of all the previously published data. At the end of this process, the experts of the CNEDiMTS (HAS) concluded that Urolift had an entire place in the therapeutic strategy of BOO treatment in France and could be used in daily practice. They assorted this statement by an ASA IV ranking corresponding to a minor improvement compared to standard treatment. They also asked the company (NEOTRACT, INC) to follow-up patients receiving Urolift in France by collecting their clinical characteristics, the number of implants used, the mid-long term functional results, and the need for any kind of retreatment.

Since then, Urolift has been sparsely used in France mainly due to the fact that the price of this single-use device is not covered by the hospitalization and that Urolift is still not reimbursed by the French Healthcare System.

In the setting of the ECOLIFT study, the Urolift device will be used following the exact recommendations of the HAS (same inclusion/exclusion criteria). The ECOLIFT protocol strictly reproduces the clinical use of Urolift without any additional clinical visit or any invasive procedure due to the research protocol as compared to French standard of care (TURP).

Additionally, the aim of our study is not to assess again its clinical effectiveness but to measure its economical value in the setting of the French Healthcare System to support the need of its reimbursement.

Finally, surgeons participating to the ECOLIFT study will have to be experienced with this procedure or to be specifically trained upfront any participation to the ECOLIFT study. Experience of at least 15 cases will be required. If the selected surgeon does not have sufficient experience, specific assistance will be provided by the company for his/her training (visit in an expert center for case observation, surgical mentoring for at least 5 cases, and 10 additional cases performed alone with possible critical review of a recorded video by an expert).

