3.2. SECONDARY OUTCOMES MEASURES

Secondary endpoints will be:

- The incremental cost/Qaly of PUL compared to transurethral surgery at 12 months
- The total hospital cost of each surgery procedure based on a top down micro-costing method performed during hospitalization stay
- Overall and specific urogenital healthcare consumptions at 4 months, 1 year and 3 years following the surgical procedure
 - Dispensed medications identified using the corresponding codes of the Anatomical Therapeutic Chemical (ATC) Classification;
 - o In- and out-patient visits;
 - Hospitalisation and their corresponding discharge diagnoses coded according to International Classification of Disease, 10th revision;
 - Medical procedures;
 - Nursing acts and physiotherapy;
 - Medical imageries and lab tests;
 - Transport;
 - Sick allowances;
 - At 4 months: all healthcare consumptions which are not reimbursed, but payed by the patient (e.g.: urinary incontinence products).

• BPH retreatment,

• Any dispensing of the following medications at 1 and 3 years after surgical procedure: alpha-blockers (ATC code G04CA) or 5-alpha-reductase inhibitors (ATC code G04CB);

 Hospitalization at 1 and 3 years after surgical procedure, with the main diagnosis of BPH (ICD-10 code N40) and the surgical procedure codes JGNE003, JGNE171, JGNJ001, JGFA005 JGFA009, JGFA015, JGFE023, JGFE365.

Urinary symptoms,

- Urinary incontinence evolution between inclusion and 4 months after surgical procedure (Incontinence Severity Index (ISI));
- International consultation on Incontinence questionnaire for Urinary incontinence short form (ICIQ-UI SF)
- Hospitalization with a discharge diagnosis ICD-10 code related to an urinary infection (code N41 for acute prostatitis or code N10 for acute pyelonephritis) at 1 and 3 years after surgical procedure;
- Hospitalization with a discharge diagnosis ICD-10 code related to urinary retention (R33) at 1 and 3 years after surgical procedure;
- Hospitalization with a discharge diagnosis ICD-10 code and/or medical procedure related to urethral stricture at 1 and 3 years after surgical procedure.

• Global quality of life,

- IPSS and IPSS-Q8 evolution between inclusion, 4 month, and 1 year after surgical procedure;
- O Jenkins sleep questionnaire between inclusion, 4 months, and 1 year after surgical procedure;
- EQ-5D-5L questionnaire (appendix 2) evolution between inclusion, 4 months, and 1 year after surgical procedure;

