5.1.2. EXCLUSION CRITERIA

- Current urinary retention
- Post void residual urine > 250ml
- Active urinary tract infection at time of treatment

- Previous BPH procedure
- Urethral conditions that may prevent insertion and delivery of device system into bladder (i.e. urethral strictures, meatal stenosis, bladder neck contracture)
- Previous pelvic surgery or irradiation
- History of neurogenic or atonic bladder
- Biopsy of the prostate within the past 6 weeks
- Life expectancy estimated to be less than 1 year
- History of prostate or bladder cancer
- PSA>10ng/ml unless prostate biopsy is negative
- Person intending to move abroad within 1 year after inclusion
- Person placed under guardianship or curatorship
- Person participating to another interventional study on benign prostatic hyperplasia during the study

Patients of the PUL and TURP/LASER cohorts will be identified in the SNDS through their NIR national identifier (if possible) or using a probabilistic linkage with age, hospital identifier (FINESS), date of hospitalization for the procedure and ICD-10 discharge diagnosis. Only patients with a 2-year history before the procedure and a 3-year follow-up after the procedure will be analyzed.

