5.2.3. MATCHING CRITERIA

A total of 5 patients will be matched to 1 patient of the PUL cohort for each procedure (TURP, HLE, GLV) according to age, date of the procedure (same month) and a high dimensional disease risk score (hDRS) based on the one-year SNDS information before the surgical procedure. The Disease Risk Score (DRS) estimates the probability of complications occurrence in the absence of the surgery of interest (PUL). DRS will be computed from a multivariable logistic regression model using a large set of variables collected during the one-year period among the SNDS cohort.

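### The SNDS comparator criteria omit PUL exclusions that claims can identify (retention, urinary infection, urethral stricture, neurogenic bladder), so the complementary PUL-versus-SNDS comparison has unequal eligibility that probably favours PUL

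*Protocol*

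**What the plan says.** **Clinical cohorts.** Section 5.1.2 applies one list of exclusions to both the PUL and the TURP/laser cohorts. It includes "Current urinary retention", "Post void residual urine > 250ml", active urinary infection at treatment, urethral conditions that block the device (strictures among them), and neurogenic or atonic bladder.

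**SNDS cohort.** Section 5.2.2 excludes patients of the 7 study centres, then "Patients with a previous BPH procedure previous pelvic surgery or irradiation, history of prostate or bladder cancer", a prostate biopsy in the preceding 6 weeks, and a Charlson index of 10 or more. Retention, infection, urethral conditions and neurogenic bladder are not listed there or in the synopsis.

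**Matching and adjustment.** Five comparators per PUL patient and per procedure are matched on age, month and a high-dimensional disease risk score built from the previous year's claims (section 5.2.3). Section 11.2.1 adds regression adjustment. Section 11.2.2 compares baseline characteristics before and after matching, with a 10% threshold for the standardised difference.

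**Outcomes.** Section 3.2 includes "Hospitalization with a discharge diagnosis ICD-10 code related to urinary retention (R33) at 1 and 3 years after surgical procedure" and parallel items for urinary infection (N10, N41) and urethral stricture.

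**Claim of comparability.** Section 1.3 describes "a matched cohort of patients identified in the SNDS database with the same baseline characteristics but treated with transurethral procedures".

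**Cost.** Section 1.6 states that "Urolift is still not reimbursed by the French Healthcare System". Section 1.1.2.3 states that "the cost of each PUL implant is about €500 and a mean of 4 implants are needed in each surgical procedure".

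**The concern.** Men with retention, infection, stricture or neurogenic bladder are removed from one arm and may remain in the other, and hospital stays for three of those four conditions are then counted. A man operated on for retention, or with a known stricture, may well be more likely to be readmitted for the same problem. Any such excess would be read as an advantage of PUL. The SNDS phase is presented as strengthening the comparison, and the synopsis says the results will support reimbursement.

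The protocol already treats retention, infection and stricture as identifiable in the SNDS, because it defines outcomes from their codes. The asymmetry is therefore only partly a limit of the data source. Cohort eligibility is fixed in section 5.2.2, so this is not a detail that the protocol leaves open.

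**Working it through.** **Step 1: the plan's own figures.**
- SNDS cohort: 80 × 5 × 3 = 1,200, as stated in section 11.1.
- Precision at n = 400, proportions, 1.96 × √(p(1−p)/n): 2.9% at p = 10% and 4.9% at p = 50%. Stated: 3% to 5%.
- Precision at n = 400, means, 1.96 × CV/√n: 5.9% at CV 0.6 and 11.8% at CV 1.2. Stated: 6% to 12%.

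The size and precision reproduce. The issue is who the 1,200 are.

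**Step 2: the two exclusion lists side by side.**

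| Condition | PUL (5.1.2) | SNDS (5.2.2) | Code used as an outcome (3.2) |
|---|---|---|---|
| Retention | excluded if current | not listed | yes, R33 |
| Urinary infection | excluded if active | not listed | yes, N10, N41 |
| Stricture and similar | excluded | not listed | yes, stricture |
| Neurogenic or atonic bladder | excluded | not listed | no |
| Residual urine > 250 ml | excluded | not listed | no; a clinical measurement |

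The first four rows can be addressed with codes. Residual urine cannot, and the same holds for the symptom score, flow rate and prostate volume that define PUL eligibility in section 5.1.1.

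**Step 3: what the safeguards reach.**
- The score uses the year before the procedure. Earlier claims can enter it, but a diagnosis coded only on the index stay is not described as entering.
- The score balances overall complication risk, not each condition. Two men can share a score when only one has retention.
- Requiring N40 as main diagnosis (section 5.2.1) does not rule out retention as an associated diagnosis.
- The balance check would show an imbalance in a recorded condition, but no consequence is fixed.

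**Step 4: illustrative size.** The protocol gives no prevalence of these conditions and no relative risk, so both are assumptions. Let f be the share of matched comparators with a PUL-excluded condition, RR their relative risk, and p₀ the event rate otherwise. Assume no true difference and no correction by matching. Then p_c = p₀(1−f) + p₀·RR·f. The base rate is taken as 20% to 40%, the range section 1.1.2.1 gives for complications of grade 2 and higher; rates for the coded outcomes may differ. The test compares 80 with 400, two-sided 5%, so the nominal chance of a significant result in PUL's favour is 2.5%.

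| p₀ | f | RR | p_c | Spurious excess (points) | Chance of significance for PUL |
|---|---|---|---|---|---|
| 20% | 5% | 1.5 | 20.5% | 0.5 | 3.1% |
| 20% | 10% | 2 | 22% | 2 | 5.5% |
| 40% | 10% | 2 | 44% | 4 | 9.5% |
| 40% | 30% | 2 | 52% | 12 | 50% |

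Example, second row: 0.20 × 0.90 + 0.40 × 0.10 = 0.22. Across f = 5% to 30% and RR = 1.5 to 2, the excess runs from 0.5 to 12 points and the chance from about 3% to 50%.

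**Step 5: the cost basis.** Section 6 describes the SNDS as reimbursed claims plus hospital-discharge data, so the unreimbursed implant is unlikely to appear in it, although the protocol does not say so. Section 7.1 gives four to six implants: 4 × €500 = €2,000 and 6 × €500 = €3,000. Against the stay income of €2,253 (section 1.1.2.3) that is 2,000/2,253 = 89% to 3,000/2,253 = 133%. The amount matters only if the index stay is counted. Section 3.2 counts consumption following the procedure, and section 9.8 dates SNDS inclusion at procedure completion. The protocol does not say whether the index stay is in or out.

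**The case against.** Several points on the other side stand.

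- **Comparators are not shown to be sicker by construction.** A reader might infer this from the lists. However, comparators are matched on age, month and a broad claims score, the analysis is adjusted, and balance is checked. Prior-year claims for these conditions are eligible inputs to the score. A residual imbalance is plausible, but its size is unknown.
- **PUL is not shown to be cheaper by construction.** A reader might infer this from the unreimbursed implant. But no cost-effectiveness ratio against the SNDS cohort is planned. Both ratios compare PUL with the TURP/laser cohort and take the index stay from micro-costing that covers materials and consumables (section 4.2). If the index stay lies outside the SNDS window, it does so for both arms.
- **Sampling other hospitals is deliberate.** Section 1.3 chooses it for generalisability, and the TURP/laser cohort supplies the same-centre comparison.
- **Hospital covariates and separate scores for retreatment or cost** are analysis-plan choices. The over-50 limit, given in the synopsis but absent from section 5.2.1, adds little because matching is on age and PUL patients are over 50.
- **A blunt exclusion would cause its own bias.** Index-stay diagnoses are settled at discharge (section 6), so an index-stay code for retention or infection may be a postoperative event, and excluding on it would delete comparator events. Excluding on any retention or infection code in the 2-year look-back would remove men whom section 5.1.2 would have accepted, because it bars only retention or infection present at the time.

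The data extraction plan may refine code lists, but it starts from section 5.2.2, which omits these conditions. The objection therefore limits the size of the point and shapes the remedy. It does not remove the mismatch.

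**Conclusion.** The point holds for eligibility. Sections 5.1.2 and 5.2.2 differ on four conditions that claims can at least partly identify. Three of them reappear as outcomes, and the statement of comparability in section 1.3 goes further than the criteria allow. The likely direction favours PUL, on the assumption that men with these conditions have more later events.

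The size cannot be derived from the protocol. The 2 to 4 points at f = 10% and RR = 2 rest on assumed inputs with no correction by matching, so they show what could be at stake and are not an estimate.

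The effect is confined to the complementary PUL-versus-SNDS comparison. The primary endpoint and the 12-month cost/QALY ratio use the TURP/laser cohort, which has the same exclusions as PUL. On cost, the protocol leaves the index stay unstated. That calls for a clear label and does not show a built-in saving.

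**What to change.** 1. In section 5.2.2, exclude SNDS patients with pre-procedure codes for urethral stricture or neurogenic bladder in the look-back, and those with retention or urinary infection codes in a short, pre-specified window before the procedure, to mirror a condition present at the time.
2. Apply the same code algorithm to the linked PUL patients, so that both arms pass the same filter.
3. Do not exclude on index-stay codes in the main analysis. Use them only in a sensitivity analysis applied to both arms.
4. Soften section 1.3: residual urine, IPSS, flow rate and prostate volume cannot be matched in claims, and outpatient claims carry no medical indication, so alignment will remain partial.
5. Label the PUL-versus-SNDS cost comparison as reimbursed consumption after the procedure. If the index stay is counted, add each PUL patient's implant cost (number used × price, about €2,000 to €3,000 at the protocol's figures).

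The cost is wording in section 5.2.2, section 1.3 and the data extraction plan, settled before extraction. The matching pool becomes somewhat smaller, out of about 60,000 procedures a year (section 1.1.2.1) for 1,200 comparators.

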9.8. SNDS ASSESSMENTS

For each patient identified in the SNDS cohort, the following settings will be defined:

- Inclusion date: date of the surgical procedure completion
- **Look-back period:** 2 years preceding the inclusion date;
- **Follow-up period:** 3 years following the inclusion date.

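### The SNDS cohort has no claims-based counterpart to the retention, stricture and neurogenic-bladder exclusions of the PUL cohort, so the PUL versus SNDS comparison of retention and stricture admissions may be confounded by baseline disease

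*Protocol*

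**What the plan says.** **Clinical cohorts (Protocol 5.1.2).** The exclusions, which apply to PUL and TURP/laser alike, include "Current urinary retention", "Urethral conditions that may prevent insertion and delivery of device system into bladder (i.e. urethral strictures, meatal stenosis, bladder neck contracture" and a history of neurogenic or atonic bladder.

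**SNDS cohort (Protocol 5.2.2).** The list covers stays in the seven study centres, "Patients with a previous BPH procedure previous pelvic surgery or irradiation, history of prostate or bladder cancer", recent prostate biopsy, and a Charlson index of 10 or more as a proxy for short life expectancy. It has no item for retention, urethral disease or bladder dysfunction.

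**Outcomes (Protocol 3.2).** Among the urinary outcomes are "Hospitalization with a discharge diagnosis ICD-10 code related to urinary retention (R33) at 1 and 3 years after surgical procedure" and "Hospitalization with a discharge diagnosis ICD-10 code and/or medical procedure related to urethral stricture at 1 and 3 years after surgical procedure".

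**Time windows (Protocol 9.8).** The inclusion date is the "date of the surgical procedure completion", the look-back is the "2 years preceding the inclusion date", and follow-up is the "3 years following the inclusion date".

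**Matching and analysis.** Section 5.2.3 matches five SNDS men per procedure type to each PUL man on age, month of procedure and a disease risk score for complications built from one year of prior claims. Section 11.2.1 plans Kaplan-Meier curves with logrank tests for retreatment and urinary events, and logistic regression adjusted for confounders that it does not name.

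**The concern.** Men with a condition are removed from one side of a comparison whose outcome is an admission for that same condition. Limits of claims data do not explain the gap. Symptom score, flow rate, residual volume and PSA results cannot be seen in the SNDS, but retention and stricture can, since section 3.2 already identifies them from hospital codes. Section 5.2.2 translates several other clinical criteria into claims, so mirroring was evidently intended and left incomplete. Section 1.3 expects the matched comparators to share the baseline characteristics of the PUL men.

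If comparators with baseline retention, stricture or bladder dysfunction are more likely to be admitted with these codes later, the SNDS event rate rises for a reason unrelated to the type of surgery, and PUL looks better than it is. Section 1.3 relies on the SNDS comparison for statistical power and generalisability, and the summary says that the results will support reimbursement.

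**Working it through.** **1. The lists side by side**

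| Condition | PUL and TURP/laser (5.1.2) | SNDS (5.2.2) | SNDS outcome (3.2) |
|---|---|---|---|
| Urinary retention | excluded if current | not excluded | yes, R33 |
| Urethral stricture | excluded if it may obstruct the device | not excluded | yes, no code listed |
| Bladder neck contracture | excluded if it may obstruct the device | not excluded | not named |
| Neurogenic or atonic bladder | excluded if in history | not excluded | not named |

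The first two rows show the direct conflict. The last two matter as possible risk factors for those outcomes.

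**2. The plan's own figures.** Section 11.1 gives the cohort sizes and precision. The SNDS size is 80 × 5 × 3 = 1200. The 95% half-width is 1.96 × √(p(1−p)/n):
- n = 400: 2.94 points at p = 10% and 4.90 at p = 50% (stated: 3% to 5%).
- n = 80: 6.57 points at p = 10% and 10.96 at p = 50% (stated: 7% to 11%).

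Both reproduce. Neither bears on bias.

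**3. Illustrative size.** Let p be the later event risk without baseline disease, q the share of comparators with baseline disease, and r their later event risk. The SNDS rate is (1−q)p + qr, so the inflation is q(r−p). The documents give none of the three. Assume p = 5% and q from 5% to 20%:

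| r | q = 5% | q = 20% |
|---|---|---|
| 5% (no excess risk) | 0 | 0 |
| 10% | 0.05 × 0.05 = 0.25 points | 0.20 × 0.05 = 1.0 points |
| 25% | 0.05 × 0.20 = 1.0 points | 0.20 × 0.20 = 4.0 points |

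Another set of assumptions, p = 10%, r = 20% and q from 10% to 30%, gives 0.10 × 0.10 = 1 point to 0.30 × 0.10 = 3 points. All these figures are before any effect of matching or adjustment.

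**4. Can the planned methods restore balance?**
- The risk score is a single number, so a man with retention can match a PUL man who reaches the same score through other conditions. Neither retention nor stricture is named as an input, and retention recorded only on the index stay lies outside the one-year window.
- Logrank tests on matched groups do not adjust further. Adjusted logistic regression helps only if these conditions are among the confounders. For current retention, which eligible PUL men should not have, it would extrapolate.
- Section 11.2.2 checks standardised differences against a 10% threshold before and after matching, but states no action if the threshold is exceeded.

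**The case against.** **Matching already targets this.** The score is meant to equalise the baseline risk of complications, and equal predicted risk from different conditions is how any disease risk score works. Balance is checked and adjusted models are planned. This stands in part: the methods may reduce the bias, and the figures above ignore them. They do not guarantee that a restriction imposed on one side only is reproduced.

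**The asymmetry is narrower than the lists suggest.** Only current retention bars a PUL man; resolved retention does not. Strictures are barred as obstacles to the device. This stands, and it shapes the fix: excluding R33 over the full two years would make the comparators cleaner than the PUL men and reverse the bias.

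**Excess risk is not established.** Surgery treats the obstruction, so a man with retention beforehand need not have a higher risk afterwards. With r = p the bias is zero. This stands; the magnitude is assumed. Even 4 points is smaller than the 6.57-point half-width for 80 PUL men at 10%, although more comparators would not reduce a bias.

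**A stronger reading fails.** A reader might infer that disease present before surgery is itself counted as a TURP/laser event. If every such case counted (r = 100%), the inflation would be 0.05 × 0.95 = 4.75 points to 0.20 × 0.95 = 19 points. The documents do not support this. An event is a hospitalisation after the procedure, and follow-up starts at its completion. The index stay must have N40 as main diagnosis (5.2.1), so R33 there would normally be an associated diagnosis, a type that section 6 says is not usually used to define outcomes. The protocol does not, however, state how index-stay codes are treated.

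**Conclusion.** The eligibility gap is real and can be read directly from 5.1.2, 5.2.2 and 3.2. Its consequence is possible confounding by baseline disease in the PUL versus SNDS comparison of retention and stricture admissions at 1 and 3 years. The direction probably favours PUL, on the assumption that men with these conditions have a higher later event risk. The size is unknown: about 0 to 4 points for q from 5% to 20%, p = 5% and r up to 25%, before any correction by the risk score or adjustment.

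Only secondary outcomes are involved. The primary cost-effectiveness endpoint compares the PUL and TURP/laser cohorts, which share the 5.1.2 criteria, so it is not affected. This is an improvement that should be made because it is cheap and the likely bias has a direction. It does not invalidate the study.

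**What to change.** 1. Add to 5.2.2 exclusions for urethral stricture, bladder neck contracture and neurogenic or atonic bladder, identified by codes in the 2-year look-back. Section 3.2 lists no stricture code and does not mention bladder neck contracture, so the codes must be specified.
2. Add R33 only within a short, pre-specified window before the index admission, to mirror current retention.
3. Apply the same code screen to the linked PUL and TURP/laser men, so that both sides face one rule. Do this before matching, since each PUL man brings 5 × 3 = 15 comparators.
4. Do not exclude on index-stay R33 in the main analysis. As section 6 describes the discharge summary, nothing dates a diagnosis relative to surgery within the stay. The code may record postoperative retention, and excluding it could remove true TURP/laser complications. Use it only in a sensitivity analysis.
5. State that index-stay codes do not count as follow-up outcomes.

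**Cost.** A few codes in the data extraction plan, which section 14.3 requires to be approved before extraction; the summary dates the first extraction to Q4 2025. Section 1.1.2.1 puts transurethral procedures at about 60,000 a year. Losing an assumed 20% would leave 60,000 × 0.80 = 48,000 a year before the other exclusions, against 1200 needed, although the split by procedure type is not given. The downside is that comparators become slightly less representative of all French practice.
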